## 6 Interim Analysis

No interim analysis planned for this study.

## 7 Efficacy and Safety Endpoints

### 7.1 Primary Efficacy Endpoints

*Change in migraine headache pain score, using an 11-point NRS, (0 = none, 10 = worst imaginable), from the time of dosing to 0.5, 1.0, 1.5, 2, 4, 8 and 24 hours post dose. Pain is recorded in a subject diary and should reflect the subject's pain at the time of recording.*

### 7.2 Secondary Efficacy Endpoints

- 1. Change in migraine-associated symptoms of nausea, photophobia and phonophobia. Symptoms are assessed on an 11- point Likert scale with 0 = no symptoms and 10 being severe symptoms at time of dosing and at 0.5, 1.0, 1.5, 2, 4, 8 and 24 hours post dose.*
- 2. Change in each subject's most troublesome symptom that may include nausea, photophobia and phonophobia cognitive impairment, dizziness and functional disability. Symptoms are assessed on an 11- point Likert scale with 0 = no symptoms and 10 being severe symptoms at time of dosing and at 0.5, 1.0, 1.5, 2, 4, 8 and 24 hours post dose.*
- 3. The percentage of subjects achieving "no headache pain" at 0.5, 1.0, 1.5, 2, 4 and 8 hours post dose.*

### 7.3 Safety Endpoints

- 1. Changes in physical examinations and vital signs*
- 2. Changes in clinical laboratory tests*
- 3. Percentage of Treatment emergent adverse events (TEAEs), including serious adverse events (SAEs), and suspected unexpected serious adverse reactions (SUSARs)*
- 4. Changes in concomitant medications*

### 7.4 Exploratory Endpoints

- 1. The percentage of subjects who are "sustained pain-free," defined as having no migraine headache pain at 24 hours, with no use of rescue medication and no relapse of headache pain within 24 hours (24-hour sustained pain-free) after administration*
- 2. The time to first pain-free timepoint following treatment with oral LAT8881 compared with placebo to 24 hours post dose, with no use of rescue medication*
- 3. Supplemental analgesic medication use in the 24 hour post treatment period*
- 4. Subject satisfaction with each treatment based on a 7-point Likert Scale, overall preference for Treatment 1 or Treatment 2, and historical comparison with usual treatment*

5. *Association between change in headache pain and symptom scores and selected subject baseline characteristics, including for example, migraine with/without aura, relationship to menstrual cycle*

## 8 Statistical Methods

Efficacy endpoints will be summarised in a descriptive manner and analysed using statistical methods described in section 11.8. Changes over time for the primary and secondary efficacy outcomes will be explored using a statistical model as defined in Section 11.8. The level of significance for any statistical tests undertaken will be 0.05 and all tests will be two-sided. Any p-values will be displayed to four decimal places, with p-values less than 0.0001 presented as '<0.0001' and p-values greater than 0.9999 presented as '>0.9999'. All analyses will be done using SAS (version 9.4, SAS Institute Inc., Cary, NC, USA).

Safety endpoints will be summarised in a descriptive manner.

Continuous data will be reported using the following descriptive statistics:

1. Number of observations (n)
2. Mean and standard deviation (SD)
3. Minimum (min) and maximum (max)
4. Median

Minimum and maximum values will be reported to the precision of the endpoint reported with maximum of three decimal places; the mean will be presented with one decimal place more and the standard deviation two decimal places more than the precision of the endpoint reported.

Categorical data will be presented using frequency (n = number of subjects; m = number of events) and percentage (%).

Listings will be provided for all data recorded in the eCRF to study subject profiles. All listings will be sorted by treatment sequence, subject ID, study period and date (if applicable). Unscheduled visit data will only be listed and not included in summaries.

### 8.1 Changes to Planned Analyses

The protocol states that, as this study is a Phase IIa proof of concept study, no formal statistical hypotheses are planned to be tested although some may be investigated as part of the data presentation. It was expected that treatment effects would be assessed using descriptive statistics only and hypothesis tests used minimally.

However, by allowing subjects to be included in the Per Protocol population with a minimum of one dose of IMP, there is a possibility that subjects will be included with efficacy results for only one treatment period and unable to have an estimate of the difference between treatments. Hence, fewer subjects will be included in the summary results and any analyses for the difference between treatments.

In order to include the results for all subjects regardless of whether they took IMP in only one or both treatment periods a mixed effects model with repeated measurements (MMRM) analysis can be undertaken. This approach will be taken for the change from baseline NRS pain score to each postbaseline timepoint for each treatment only.

The remaining endpoints of a continuous nature (change from baseline NRS symptom score, change from baseline NRS symptom score for the most troublesome symptom, subject satisfaction with IMP, subject satisfaction with IMP compared with usual medication for an acute migraine attack) may be analysed using the MMRM approach depending on the number of subjects who complete both treatment periods. The decision will be made at the blind review meeting prior to database lock.

## 8.2 Handling Missing/Incomplete Data

Partial dates will not be imputed.

Flags identifying the study period for the start/stop dates for prior/ concomitant medications and adverse events will be generated (see Sections 10.9 and 10.10).

The method for missing data imputation for the primary endpoint will be discussed during the blinded review meeting prior to database lock.

## 8.3 Handling Outliers

Laboratory results with modifiers will be analysed with the maximum or minimum value defined without the modifiers. For example, a value of “<5” will be considered as “5” for summaries.

## 8.4 Multiplicity Adjustment

Since there is only one primary endpoint defined in the study as per the protocol, multiplicity adjustment is not required. Although, hypothesis tests will be performed caution must be taken when interpreting these results. Adjusted p-values using Bonferroni method may be derived for post-hoc analyses if deemed necessary.

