10.1 Primary endpoint

Change in migraine headache pain score, using an 11-point NRS, (0 = none, 10 = worst imaginable), from the time of dosing (t = 0 min) to 0.5, 1.0, 1.5, 2, 4, 8 and 24 hours post dose. Pain is recorded in a subject diary and should reflect the subject's pain at the time of recording.

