## 11 Statistical Analyses

Summaries will be based on treatment sequence for the following:

- Subject Disposition
- Demographic and Baseline Characteristics
- Prior Medications
- Medical / Surgical History

“Total” columns will be included in these summaries. For all other analyses, summaries will be based on treatment overall and within study periods.

Following conventions will be used for the choice of treatment sequence / group in summaries:

- FAS Population – Planned treatment sequence / group
- Safety Population – Actual treatment sequence / group
- Per-protocol Population – Actual treatment sequence / group

Number of analysis to be done on the primary and secondary endpoints will be confirmed based on subjects exposed to IMP at blinded review meeting.

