#### 11.8.1.3 Mixed Effect Regression Model for repeated measurements (MMRM)

A mixed effects regression model using a covariance pattern will be fitted to the absolute change from baseline in NRS pain scores at each post-IMP timepoint within each treatment period for the PP population.

The model will have fixed effects for treatment period, timepoint, treatment and the interaction between timepoint and treatment. Baseline pain score within each period will be included as a covariate. A random effect for subject will be included to capture the repeated measures nature of the design.

Least squares means and corresponding 95% confidence intervals (CI) will be presented for the mean changes from baseline for LAT8881, Placebo and the difference between LAT8881 vs. placebo at each timepoint. P-values for testing the null hypothesis that the difference in least squares means between LAT8881 and placebo at each timepoint is 0 will be declared statistically significant if the p-value <0.05.

The covariance pattern will take into account the covariance between observations in different treatment periods and the covariance between observations within the same period (i.e. between timepoints).

```
proc mixed data=; class <subject> <study period>  
<treatment> <timepoint>; model <change> = <baseline> <study  
period> <timepoint>|<treatment>; random <subject>  
<subject>*<period>; lsmeans <treatment>|<timepoint> / pdiff;  
run;
```

In DDP: Tables 14.2.1.5

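### The reason SAP 8.4 gives for waiving multiplicity adjustment does not hold: the single primary endpoint is tested at seven times, each labelled significant at p<0.05, with no contrast designated primary

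*SAP*

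**What the plan says.** SAP 8.4 gives one reason for not adjusting: "Since there is only one primary endpoint defined in the study as per the protocol, multiplicity adjustment is not required". It then warns that although "hypothesis tests will be performed caution must be taken when interpreting these results", and adds: "Adjusted p-values using Bonferroni method may be derived for post-hoc analyses if deemed necessary".

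The endpoint it refers to is the change in the 11-point pain score. Protocol 10.1 measures it "from the time of dosing (t = 0 min) to 0.5, 1.0, 1.5, 2, 4, 8 and 24 hours post dose", and SAP 7.1 does the same, "from the time of dosing to 0.5, 1.0, 1.5, 2, 4, 8 and 24 hours post dose". Neither document singles out one time.

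SAP 11.8.1.3 fits a mixed model and reports a LAT8881–placebo difference, 95% CI and p-value at every post-dose time. The p-value for the null hypothesis that the difference "at each timepoint is 0 will be declared statistically significant if the p-value <0.05". SAP 8 sets every test at 0.05, two-sided. There is no hierarchy, global test or adjustment across the seven times.

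Protocol 14.1 and the protocol synopsis specify no formal hypotheses, but both say that p<0.05 will be called statistically significant for any comparison that is tested.

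**The concern.** One endpoint name is not one test. Multiplicity arises from the number of comparisons that can earn a significance label, and here there are seven, any of which can earn it alone. A reader of the final report who sees a labelled timepoint, and reads in the SAP that no adjustment was needed, would reasonably take the label to carry a 5% false-positive risk. It does not. What is at stake is how the primary result of a proof-of-concept study is read.

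**Working it through.** **Plan's own figures.** The documents state no familywise error rate and no power, so there is none to reproduce. The one computable design figure is enrolment: 20 / (1 − 0.20) = 25, against 26 planned. Only the 20 completers enter the check below.

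**Inputs**
- Number of tests: k = 7 (Protocol 10.1, SAP 7.1).
- Level: 0.05 two-sided per test (SAP 8, SAP 11.8.1.3).
- Completers: n = 20 (SAP 4.2).
- Correlation ρ between the within-subject treatment differences at two times: not in the documents. Assumed 0.5 to 0.95.

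**Correlation form.** The code in SAP 11.8.1.3 has random effects for subject and subject-by-period and no REPEATED statement. In a within-subject difference the subject effect cancels. The subject-by-period part is common to all seven times and the residual is not. So ρ = σ²(subject×period) / [σ²(subject×period) + σ²(residual)], the same for every pair of times, which is exchangeable. Real pain scores within an attack may decay in correlation over time, so AR(1) in timepoint order is shown as well.

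**Step 1, independence, as a ceiling only.** 1 − 0.95^7 = 0.302. This is not realistic within one attack.

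**Step 2, large-sample, exchangeable.** With c = 1.96:

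P(at least one) = 1 − ∫ φ(x) [Φ((c − √ρ·x)/√(1−ρ)) − Φ((−c − √ρ·x)/√(1−ρ))]^7 dx

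This gives 23.0% at ρ = 0.5, 17.8% at 0.7, 11.4% at 0.9 and 9.2% at 0.95.

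**Step 3, n = 20.** Paired t-tests, no effect, simulated with 300,000 trials per cell:

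| ρ | Exchangeable: any p<0.05 | of which any favouring LAT8881 | AR(1): any p<0.05 | of which any favouring LAT8881 |
|---|---|---|---|---|
| 0.5 | 23.4% | 11.8% | 26.9% | 13.8% |
| 0.7 | 18.4% | 9.3% | 23.0% | 11.7% |
| 0.9 | 11.9% | 6.0% | 15.1% | 7.5% |
| 0.95 | 9.5% | 4.7% | 11.9% | 5.9% |

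The nominal values for a single test are 5% and 2.5%.

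**Step 4, the SAP's random effects.** With complete balanced data, a period effect and no baseline covariate (40,000 trials), the exchangeable range for ρ = 0.95 to 0.5 is 9.1% to 22.6% with Satterthwaite degrees of freedom and 11.2% to 24.0% with residual degrees of freedom. Under AR(1) data it is 11.2% to 26.6% and 13.3% to 27.1%. Leaving out the baseline covariate is a simplification.

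**Step 5, whether other text changes the result.**
- The caution sentence in 8.4 leaves the label in 11.8.1.3 in place.
- The Bonferroni sentence is optional and concerns post-hoc analyses; the seven tests are planned.
- SAP 11 says: "Number of analysis to be done on the primary and secondary endpoints will be confirmed based on subjects exposed to IMP". That concerns how many analyses are run. It does not say how several tests would be labelled.
- The code line "lsmeans <treatment>|<timepoint> / pdiff" also produces an overall treatment contrast, but nothing makes that contrast primary.

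**The case against.** The strongest reply is that this is an unpowered, exploratory study. The protocol specifies no formal hypotheses, and SAP 8.1 brings in the mixed model to keep subjects dosed in only one period, not to create a confirmatory test. SAP 8.4 itself urges caution, all seven differences are shown with 95% CIs, and nothing treats success at any one of seven times as a criterion. All of this stands, and it limits the consequence. It does not rescue the stated reason. An exploratory defence fits a plan that reports estimates without labels; this plan states a null hypothesis and applies a label at each time.

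Two further replies have some force. The term post-hoc in 8.4 is not defined and could loosely cover comparisons of least squares means after a model fit. Even so, the adjustment would be optional. And the p<0.05 label begins in the protocol, so the SAP is following it. That matters for the fix, which must be recorded as a change.

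Three stronger readings are tempting, and the documents do not support them:
- **That the trial has a false-positive rate of 27% or 30%.** The 30% needs independent timepoints. The 27% belongs to AR(1) at ρ = 0.5, not to the exchangeable form the code implies. The low end of one structure should not be joined to the high end of the other.
- **That a wrong development decision follows.** No decision rule in either document depends on a p-value.
- **That the blinded review is already charged with choosing a primary contrast.** The sentence in SAP 11 covers only the number of analyses.

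**Conclusion.** The point holds in a limited form. The reason given in SAP 8.4 is wrong as written, because one endpoint here means seven planned tests, each with its own significance label. With no effect and 20 completers, the two-sided chance of at least one label is about 10% to 23% (exchangeable) or 12% to 27% (AR(1)), for an assumed ρ of 0.95 to 0.5. It exceeds 5% in every case tried.

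These figures are for at least one labelled time. They are not the chance of exactly one, which is smaller: about 2.6% at ρ = 0.95 and 16% at ρ = 0.5 under exchangeable correlation.

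This is a misleading label, not a failed decision rule. It should be corrected because correction is cheap, but its weight is minor to moderate.

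**What to change.** Make the change before database lock and unblinding, and record it in SAP 8.1 as a departure from the p<0.05 labelling in Protocol 14.1 and the synopsis.

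1. In SAP 8.4, replace the reason. For example: *The single primary endpoint is tested at seven post-dose times; the p-values for the individual times are nominal and are not controlled for multiplicity.*
2. In SAP 11.8.1.3, and in the general 0.05 statement in SAP 8, choose one of:
   - **(a)** Designate one mixed-model LAT8881–placebo contrast as primary, carrying the only p<0.05 label. Report the others as unlabelled estimates, 95% CIs and nominal p-values. Name the degrees-of-freedom method as well: in the simulations a single contrast (2 hours or overall) rejected 4.9% to 6.6% of the time with residual degrees of freedom and 4.8% to 5.2% with Satterthwaite.
   - **(b)** Drop the significance label from all seven contrasts.

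Holm adjustment is optional, if the team wants a label available at any time. Apply it only to the seven same-time LAT8881–placebo p-values. The code line requests 1 + 21 + 91 = 113 comparisons, and adjusting over the 91 would be needlessly severe.

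**Cost.** SAP wording, plus one short programming step if Holm is used; no new data or subjects. Under (a) a result at any other time is only supportive. Under (b) there is no significance claim. Under Holm the smallest p-value must be below 0.05/7 = 0.0071. With 20 pairs, an effect of 0.66 SD of the paired difference at one time only has 80% power unadjusted and about 49% under Holm. That loss is why Holm should not be mandatory here.

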# 9 Analysis Populations

Membership of the analysis populations will be reviewed and finalised during the blind review of the data conducted prior to database lock.

## 9.1 Full Analysis Set (FAS)

*The Full analysis set (FAS) consists of all subjects enrolled and randomised into the study.*

*The FAS population will be used for summaries of subject disposition, demographic and baseline characteristics. Subjects will be analysed according to the treatment group they were assigned at randomisation.*

## 9.2 Per Protocol (PP) Population

The Per Protocol (PP) population will include all subjects who received at least one dose of IMP and excludes subjects who have any major protocol deviation impacting the study endpoints. Deviations

for exclusion from the PP population due to inadequate exposure to IMP or completeness of primary efficacy endpoint will be determined during the blinded review meeting prior to database lock.

*A per-protocol (PP) population will be used for efficacy analyses and to analyse exploratory endpoints.*

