14.3.2 Per protocol population

A per-protocol (PP) population will be used for efficacy analyses and to analyse exploratory endpoints. The PP population will be based on IMP exposure, including the time of any episodes of vomiting and major protocol deviations.

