### 10.15.3 Time Deviated from Scheduled Timepoints

Actual time difference from ‘Time IMP was taken’ to each of the timepoints will be calculated and discussed during blinded review meeting and any analysis flags may be created to exclude the same.

Time deviated (hours) = (Time the corresponding timepoint recorded - Time IMP was taken) / 60.

Time difference between pre-dose measurement and IMP dosing should not be more than 30 mins. This difference will also be highlighted in the blinded review meeting.

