## 11.2 Protocol Deviations

Number and percentage of subjects with any deviation and number of deviation events will be summarised by treatment within each study period. The same will be sub-classified by category (major/minor) and description as follows:

- Inclusion / Exclusion
- Investigational Product
- Concomitant medications
- Laboratory tests
- Visit Schedule
- Procedures / Tests
- Randomisation
- Safety Reporting
- Protocol Specific Discontinuation Criteria
- Other

Deviation categories will be displayed in the descending order of frequency of total number of deviations in LAT8881 group (both study periods combined). Percentages will be based on FAS population. Protocol deviations occurring between Visit 2 and Visit 3 will be counted in Period 1, and those occurring after Visit 3 will be counted in Period 2.

In DDP: Table 14.1.2

Protocol deviations will be listed by subject.

In DDP: Listing 16.2.2

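### SAP 9.2 excludes whole subjects from the per-protocol set, so a major deviation confined to one attack also removes the subject's unaffected period from the primary mixed model

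*SAP*

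**What the plan says.** SAP 9.2 builds the PP population in two steps. It "will include all subjects who received at least one dose of IMP", and it "excludes subjects who have any major protocol deviation impacting the study endpoints". Both steps are worded by subject. SAP 10.1 takes the population flags from the section 9 definitions, so the flag follows the subject too.

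Some of the detail is left open. Under SAP 9.2, the events that count "for exclusion from the PP population due to inadequate exposure to IMP or completeness of primary efficacy endpoint will be determined during the blinded review". Protocol 14.3.2 is more specific about the criteria: "The PP population will be based on IMP exposure, including the time of any episodes of vomiting and major protocol deviations".

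SAP 8.1 explains why a mixed model was added: "In order to include the results for all subjects regardless of whether they took IMP in only one or both treatment periods". SAP 11.8.1.3 fits that model to change in pain score "at each post-IMP timepoint within each treatment period for the PP population". No version on the full analysis set (FAS) is specified. SAP 11.8 leaves even descriptive FAS efficacy summaries to the blind review, whereas protocol 14.5 says that all efficacy tables and results will be shown for the FAS as well as for PP.

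Two other places work below subject level. For the deviation table in SAP 11.2, "Protocol deviations occurring between Visit 2 and Visit 3 will be counted in Period 1", and later ones go to Period 2. For diary entries recorded off schedule, SAP 10.15.3 says that "any analysis flags may be created to exclude the same".

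**The concern.** The unit of treatment is the attack. Inadequate exposure, a dose taken outside the allowed time, or a disallowed medicine before one dose spoils that attack and says nothing about the other. Under SAP 9.2 as worded, any of these, if classed as major, removes both attacks.

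The model does not need this. It is built to accept a subject with a single period, and SAP 8.1 gives that as the reason for using it. The result is uneven: a subject who never took the second dose contributes one period, while a subject who took both doses, one of them with a major deviation, contributes none.

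At stake are valid attacks in a trial planned around 20 completers. Because the model is specified on PP only, a period lost from PP is lost from the only model-based analysis of the primary endpoint.

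**Working it through.** **The plan's own sizing.** There is no power calculation to reproduce (protocol 14.2). The only figure is 26 enrolled to give 20 completers with up to 20% non-completion: 20 / (1 − 0.20) = 25, against 26 stated. That is close and not at issue. I use 20 two-period subjects below.

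**Assumptions.** The documents give neither a rate of major deviations nor a correlation between a subject's two attacks. I assume a probability q of a major deviation in each attack, independent between attacks, and a within-subject correlation rho. Both are varied.

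**Step 1: unaffected periods discarded.** Among 20 subjects, the expected number with exactly one affected attack is 20 × 2q(1 − q). Each loses one unaffected period under SAP 9.2.

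| q | Subjects kept, 20(1 − q)² | Unaffected periods lost | Periods kept, by subject | Periods kept, by period |
|---|---|---|---|---|
| 5% | 18.1 | 1.9 | 36.1 | 38.0 |
| 10% | 16.2 | 3.6 | 32.4 | 36.0 |
| 20% | 12.8 | 6.4 | 25.6 | 32.0 |

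**Step 2: precision at one timepoint.** Take unit variance, fixed period and treatment effects, and balance over sequence. Let k of the 20 subjects have one affected attack, spread evenly over period and treatment.

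- Information from the 20 − k complete pairs: (20 − k) / [2(1 − rho)].
- Information added by k retained single periods: k / 4.
- SE ratio, by-period over by-subject = √[pairs / (pairs + singles)].

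| k | rho | Pairs | Singles | SE ratio | SE reduction |
|---|---|---|---|---|---|
| 2 | 0.5 | 18 / 1.0 = 18.00 | 0.5 | √(18 / 18.5) = 0.986 | 1.4% |
| 2 | 0.2 | 18 / 1.6 = 11.25 | 0.5 | √(11.25 / 11.75) = 0.978 | 2.2% |
| 4 | 0.5 | 16 / 1.0 = 16.00 | 1.0 | √(16 / 17) = 0.970 | 3.0% |
| 4 | 0.2 | 16 / 1.6 = 10.00 | 1.0 | √(10 / 11) = 0.953 | 4.7% |
| 8 | 0.5 | 12 / 1.0 = 12.00 | 2.0 | √(12 / 14) = 0.926 | 7.4% |
| 8 | 0.2 | 12 / 1.6 = 7.50 | 2.0 | √(7.5 / 9.5) = 0.889 | 11.1% |

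A generalised least squares calculation with period effects gives the same values. At rho = 0.7 and k = 4 the reduction falls to 1.8%, because a single period adds only between-subject information. The k = 8 rows need 40% of two-period subjects to have a one-attack major deviation.

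**Step 3: does excluding by period reduce bias?** If exclusion is unrelated to the score, both rules are unbiased. Now take an extreme case: no true difference, unit SD, and only the worst 20% of placebo attacks excluded.

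- The cut lies at 0.842 SD, where the normal density is 0.280. The mean of the remaining placebo scores shifts by 0.280 / 0.80 = 0.350 SD.
- By subject, the active mean shifts by rho × 0.350. Bias = 0.350(1 − rho) = 0.175 SD at rho 0.5.
- By period, all active scores stay and the model adjusts placebo through rho. Bias = 0.350(1 − rho²) = 0.26 SD at rho 0.5.

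Simulation agrees (about 0.17 and 0.26). Neither rule removes the selection, and in this case the period-level rule is the worse of the two.

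**The case against.** The strongest reply is that SAP 8.1 speaks of subjects who took IMP in one period, not of subjects with one usable period. Keeping people who did not dose twice while excluding major deviators is an ordinary per-protocol choice. That stands: a reader might infer that 9.2 contradicts 8.1, and the text does not go that far. Extending the purpose of 8.1 to a subject with one unaffected attack is an inference. It is a reasonable one, since the model receives the same data, but no more.

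A second reply is that the SAP does not name which events are major, and that the blinded review finalises PP membership and may flag off-schedule diary entries. This stands in part. The review could decide to exclude by period. What 9.2 hands to it, though, is which exposure or completeness deviations lead to exclusion, and no text provides for dropping one period of a subject. A missing pre-dose score should not be counted as a trigger, because SAP 10.12.2 sends it to the review so that a baseline can be defined.

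Third, the gain is small and reaches few analyses. Retained single periods enter the mixed model and the by-treatment summaries. They add nothing to the paired differences (SAP 10.15.1), the two-way pain-free tables (10.16) or the paired satisfaction test (11.8.3.3). This stands in full.

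Last, a reader might infer that keeping the unaffected period also makes the comparison fairer. Step 3 shows otherwise. When exclusion depends on the attack's own outcome, as it may with early rescue or vomiting, either PP rule is biased, and excluding by period can be more so.

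**Conclusion.** The point holds on consistency and precision only, and is minor. As worded, SAP 9.2 costs a subject both periods for a major deviation in one attack, while a subject who dosed once is kept in the same model. The standard error would be about 1% to 5% smaller under period-level exclusion with 2 to 4 of 20 two-period subjects affected. That rests on an assumed rho of 0.5 to 0.2, balanced deviations and a single-timepoint calculation; the documents supply neither the rate nor the correlation. In an exploratory trial without a formal sample size, a gain of this size would rarely change a conclusion. Exclusion of the whole subject remains right where a deviation affects both periods, such as ineligibility. No claim of reduced bias is supported, so the change should come with an FAS version of the model.

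**What to change.** Amend SAP 9.2 along these lines, for the mixed model and the by-treatment summaries:

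> PP membership is defined by subject and treatment period. A period is excluded if a major deviation affecting the endpoints occurred in it (for example inadequate exposure, a dose-timing deviation, or prohibited medication before that dose). The subject's other period is retained. The whole subject is excluded only for deviations that affect both periods, such as failure of an eligibility criterion.

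Carry one PP flag per subject-period in SAP 10.1, and settle the list of qualifying deviations at the blinded review under this rule.

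In SAP 11.8.1.3, present the same model on all dosed periods of the FAS. This is consistent with protocol 14.5 and gives a result that does not depend on PP exclusions linked to the attack's own outcome.

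The cost is a short paragraph, one flag and one further run of an existing model, all before database lock and with no new data. SAP 11.2 already assigns deviations to periods. The paired-difference tables and the model will show different numbers of subjects, as they already must when someone doses only once. The two arms of the PP model may also contain partly different subjects, which is a further reason to show the FAS result beside it.
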